- For each binary secondary endpoint except for UC-related hospitalization, the estimand is the difference in the proportion of subjects achieving the endpoint regardless of premature discontinuation of study drug and without initiation or dose escalation of UC-related corticosteroids and without UC-related surgery (ileostomy, colectomy, or proctocolectomy) (see Section 8.0) between risankizumab 1200 mg IV and placebo in the ITT2 population.
- For occurrence of UC-related hospitalization, the estimand is the difference in the proportion of subjects having UC-related hospitalization through Week 12 regardless of premature discontinuation of study drug and regardless of initiation or dose escalation of UC-related corticosteroids or UC-related surgery (ileostomy, colectomy, or proctocolectomy) (See Section 8.0) between risankizumab 1200 mg IV and placebo in the ITT2 population.
- For each continuous secondary endpoint, the estimand is the difference in the mean change from baseline of the endpoint regardless of premature discontinuation of study drug and without initiation or dose escalation of UC-related corticosteroids and without UC-related surgery (ileostomy, colectomy, or proctocolectomy) (See Section 8.0) between risankizumab 1200 mg IV and placebo in the ITT2 population.

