- Subjects will then be characterized as responders or non-responders based on MI imputed datasets. Using the CMH model adjusted by stratification factors (Advanced Therapies-IR status (yes vs no), baseline steroid use (yes vs no), and baseline Adapted Mayo score (≤ 7 vs > 7)), the imputed endpoints will be analyzed using each of the 30 datasets. SAS PROC MIANALYZE will be used to generate the final inferences of the risk difference between risankizumab treatment group and placebo group, using Rubin's rule. Note that measurements will be set to missing on or after the date of the UC-related corticosteroids intercurrent event or the occurrence of the UC-related surgery before applying MI. After the MI imputation, an NRI override will be implemented for missing values 1) due to reasons other than COVID-19 infection or logistic reasons or geo-political conflict in Ukraine or surrounding area, or 2) on or after the date of the UC-related corticosteroids intercurrent event, or 3) on or after or the date of the

UC-related surgery intercurrent event. That is, regardless of MI imputed values, subjects satisfying 1) or 2) will be considered as "non-responder" for binary efficacy endpoints.

- For binary efficacy endpoints of occurrence of hospitalization and the occurrence of UC-related surgeries, As Observed (AO) analysis will be used.
 - As Observed: The AO analysis will not impute values for missing evaluations, and thus a subject who does not have an evaluation on a scheduled visit will be excluded from the AO analysis for that visit. AO will include all values collected in the study regardless of intercurrent events.
- Tipping Point Analysis for Binary Endpoints

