UC-related hospitalizations through Week 12	Risankizumab 1200 mg IV vs. placebo	Occurrence of UC-related hospitalization through Week 12	ITT2	IE1: premature discontinuation of study drug IE2: initiation or dose escalation of UC-related corticosteroids IE3: occurrence of the UC-related surgery (ileostomy, colectomy, or proctocolectomy) All data after IE1 will be used. All data after IE2 or IE3 will be used.	Proportion of subjects having at least one UC-related hospitalization through Week 12

The binary secondary endpoints will be analyzed based on ITT2 using the same approach as that for primary endpoint as specified in Section 9.3.2. Specifically, CMH adjusting for stratification factors will be used to construct the treatment difference, the associated

95% CI and p-value between risankizumab 1200 mg IV group and placebo group. The NRI-MI will be the primary approach for missing data handling in the analyses of binary secondary efficacy endpoints except for Occurrence of UC-related hospitalization, of which AO data will be used.

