For UC-related hospitalizations through Week 12, to consider Missing-Not-At-Random (MNAR) assumption due to different dropout rates between treatment groups, a supplementary analysis will be performed based on exposure adjusted occurrence of UC-related hospitalizations through Week 12. Exposure adjusted occurrence of UC-related hospitalization will be analyzed based on incidence rates. Incidence rates for hospitalization will be calculated as the number of patients with the respective event divided by the time at risk. For patients with an event during the study period, time at risk is the patient-years (PYs) from the first dose date to the first event before Week 12. For patients without an event during Period 1, time at risk is PYs from first dose date to the end of study follow-up period, where the follow-up period starts from the first dose date to the last dose date in Period 1+ 140 days if prematurely discontinues the study drug without entering Period 2 or M16-066, or the first dose date of Period 2 or M16-066 if enters Period 2 or M16-066, whichever occurs earlier. The event date is defined as the date of admission to the hospital for hospitalizations. The incidence rate difference, 95% CI and p-value are calculated to evaluate the statistical significance of the difference between risankizumab 1200 mg IV group and placebo group using normal approximation to Poisson distribution. The analysis will be based on the AO data.

The continuous secondary endpoints will be analyzed based on ITT2 by RTB-MI with MMRM (for endpoints with more than one post-baseline visits) or with ANCOVA (for endpoints with one post-baseline visit) and the corresponding analyses are specified in Section 9.2.2. The least square (LS) mean and 95% CI for each randomized treatment group and the LS mean treatment difference, the associated 95% CI and the p-value between risankizumab 1200 mg IV group and the placebo group will be provided. Considering unequal variances due to the unequal sample size in the two treatment groups (2:1 randomization), a sensitivity analysis will be performed for continuous secondary

endpoints with only a single post-baseline measure using an ANCOVA model that estimates variance by treatment group.

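### UC-related hospitalization through Week 12 is an event dated by admission but gets a visit-based As Observed exclusion, so its denominator is unclear and can depart from ITT2

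*SAP*

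**What the plan says.** SAP 9.2.1 takes hospitalization and UC-related surgery out of the NRI-MI approach and assigns them to As Observed (AO) analysis. AO is defined in two parts. The first is an exclusion: "a subject who does not have an evaluation on a scheduled visit will be excluded from the AO analysis for that visit". The second is an inclusion: "AO will include all values collected in the study regardless of intercurrent events". Protocol 8.1.2 has the same two parts.

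The endpoint in SAP 9.4.2, Table 2 is "Proportion of subjects having at least one UC-related hospitalization through Week 12". For dating, the same section says: "The event date is defined as the date of admission to the hospital for hospitalizations". In SAP 2.1, "the estimand is the difference in the proportion of subjects having UC-related hospitalization through Week 12 regardless of premature discontinuation of study drug", and also regardless of steroid change or UC-related surgery, in ITT2. SAP 4.0 defines ITT2 as every randomized subject who received at least one dose in Induction Period 1.

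SAP 9.4.2 also plans an exposure-adjusted supplementary analysis, introduced with the words "to consider Missing-Not-At-Random (MNAR) assumption due to different dropout rates between treatment groups". It too is based on AO data. SAP 13.0 places this endpoint in the second group of secondary endpoints, tested by the Holm procedure.

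**The concern.** A rule that removes a subject for lacking an evaluation suits a score measured at a visit. Hospitalization is a yes/no event over an interval, known from an admission date. The documents do not say which evaluation triggers exclusion for this endpoint, whether a premature discontinuation visit would satisfy it, or how a subject who leaves before Week 12 is classified, with or without a prior admission.

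At stake is the denominator, and possibly the numerator, of a formally tested endpoint with few expected events. Admission for UC is a plausible reason to leave a trial, and so is lack of efficacy without admission. Dropping the first kind of leaver removes events. Dropping the second kind removes event-free subjects, probably more of them on placebo. These push the estimate in opposite directions.

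**Working it through.** **No stated figure to reproduce.** Neither document gives a hospitalization rate, a dropout rate or power for this endpoint. The arm sizes are 322 placebo and 644 risankizumab (SAP 2.4). All rates below are assumptions.

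**Formula.** Let p be the true hospitalization rate, q the share of admitted subjects with no scheduled evaluation, and d the share of never-admitted subjects with none. Literal exclusion estimates

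rate = p(1 - q) / [p(1 - q) + (1 - p)(1 - d)].

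With all ITT2 subjects in the denominator and all admissions recorded, the rate is p.

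**Worked case.** p = 5% placebo and 2% risankizumab, q = 50%, d = 10% and 3%:

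- Placebo: 0.025 / (0.025 + 0.95 × 0.90) = 0.025 / 0.880 = 2.84%
- Risankizumab: 0.010 / (0.010 + 0.98 × 0.97) = 0.010 / 0.9606 = 1.04%
- Difference: -1.80 points instead of -3.00
- Subjects analysed: 322 × 0.880 = 283 and 644 × 0.9606 = 619
- Admissions dropped: 322 × 0.05 × 0.5 = 8.1 of about 16 on placebo, and 644 × 0.02 × 0.5 = 6.4 of about 13 on risankizumab

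**Range for a true difference of -3.0 points** (5% vs 2%). Power is a two-proportion normal approximation at two-sided 0.05, for scale only.

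| q | d (placebo/risankizumab) | Placebo | Risankizumab | Difference | Power |
|---|---|---|---|---|---|
| All ITT2 counted | none excluded | 5.00% | 2.00% | -3.00 | 70.5% |
| 0% | 15% / 5% | 5.83% | 2.10% | -3.73 | 78.5% |
| 0% | 10% / 3% | 5.52% | 2.06% | -3.46 | 76.1% |
| 30% | 10% / 3% | 3.93% | 1.45% | -2.48 | 63.0% |
| 50% | 10% / 3% | 2.84% | 1.04% | -1.80 | 51.2% |
| 80% | 10% / 3% | 1.16% | 0.42% | -0.74 | 28.2% |

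The q = 0 rows show what happens if every recorded admission is kept and only event-free leavers are excluded: the difference is enlarged. In the other rows admitted leavers are excluded as well, and it shrinks.

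**Other assumed rates**, over the same q (0 to 80%) and both d pairs: 3% vs 1% (true -2.0) gives -0.47 to -2.46; 5% vs 1% (true -4.0) gives -0.95 to -4.78; 8% vs 2% (true -6.0) gives -1.48 to -7.18.

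**The supplementary analysis.** Events count only before Week 12 (12 × 7 = 84 days). An event-free subject who stops drug and enters neither Period 2 nor M16-066 accrues time at risk to last dose + 140 days. That is 0 + 140 = 140 days after a single dose and 56 + 140 = 196 days after a Week 8 dose. Such subjects add person-time in which no event can count, which lowers the rate most in the arm with more early stopping.

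**The case against.** The strongest reply is that the AO definition must be read whole. A dated admission is a collected value, and the second sentence of the definition keeps all collected values. The exclusion is confined to a particular visit, and this endpoint belongs to none. SAP 9.4.2 uses AO data while giving early leavers time at risk, so in the SAP's own usage AO does not discard them. Data collection does not end with a missed visit either: admission is an SAE criterion reportable within 24 hours of site awareness (Protocol 6.1.1.2), and adverse events are collected to 140 days after last dose (Protocol 6.1.4), beyond Day 84 even after one Day 0 dose.

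Most of this stands. It makes loss of recorded admissions one reading, not a requirement of the text. It does not settle the denominator. The inclusion sentence speaks of intercurrent events, which SAP 8.0 limits to drug discontinuation, steroid change and UC-related surgery; a missed visit or study withdrawal is none of these. Protocol 8.1.2 attaches the same exclusion to Observed Cases, and AO differs only by the added sentence, so that sentence does not clearly cancel the exclusion. Even if every admission is kept, event-free leavers may still be excluded, which is the q = 0 case above. The exposure-adjusted analysis is supplementary, rests on the same AO data and has the time-at-risk mismatch shown above.

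A reader might infer that the plan removes subjects who were hospitalised and then left, and so contradicts its own estimand. The documents do not support that. For drug discontinuation, steroid change and surgery the estimand and AO agree: Table 2 says "All data after IE2 or IE3 will be used". Study withdrawal is not a listed intercurrent event. What follows is an unstated denominator and a possible mismatch with ITT2.

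**Conclusion.** The concern holds as a mismatch between rule and endpoint. A visit-based exclusion is prescribed for a cumulative event, and applied literally it yields an analysed set that can be smaller than ITT2. On assumed rates of 5% and 2%, with 0 to 80% of admitted subjects and 10%/3% or 15%/5% of the others lacking the evaluation, a true -3.0 points is estimated as anything from about -0.7 to -3.7. A reader might infer a fixed direction, with the difference always shrunk. That does not follow: the direction depends on whether admitted or only event-free leavers are dropped.

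The size rests entirely on assumed hospitalization and dropout rates. The power figures use a nominal 0.05; Figure 3 of the SAP is not shown, so the alpha reaching this endpoint cannot be computed. The primary endpoint and the first ten secondary endpoints do not use this rule.

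**What to change.** In SAP 9.2.1 and 9.4.2, replace the exclusion sentence for this endpoint with a rule that:

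- keeps all ITT2 subjects in the denominator;
- counts as an event any UC-related admission dated from first dose to the earliest of Day 84, first Period 2 dose or first M16-066 dose, whether or not a Week 12 evaluation exists, using the SAE data collected to 140 days after last dose;
- states that event-free early leavers count as event-free in the main analysis.

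Keep the stratified CMH risk difference as the main analysis. Add a Day 84 Kaplan-Meier cumulative incidence difference as a sensitivity analysis for subjects lost before Day 84. It assumes non-informative censoring, which is doubtful if leaving is related to worsening UC, so it should not replace the CMH analysis. In the supplementary rate analysis, end time at risk no later than Day 84 so that it matches the event window.

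The cost is a few lines of SAP text and one time-to-first-admission derivation. No new data are needed, since the SAP already uses admission dates. The wording should be settled before unblinding.

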9.2.2 Continuous Endpoints

- The primary approach for handling missing data in the analysis of continuous endpoints will use Multiple Imputation incorporating Return-to-Baseline (RTB-MI) to handle visits on or after the date of UC-related corticosteroids intercurrent event (IE2) or on or after the date of the UC-related surgery (IE3). To handle the potential departures from the missing-at-random (MAR) assumption for visits on or after the date of IE2 or IE3 (see Section 8.0), the Return-to-Baseline (RTB)^{5,6} approach which assumes subjects with initiation or dose escalation of UC-related corticosteroids or with UC-related surgery (ileostomy, colectomy, or proctocolectomy) will have a washout "return to baseline" of any potential treatment effect, will be performed as following:
 - Step 1: after setting data on or after the date of IE2 or IE3 as missing.
 - Step 2: subject's efficacy assessments on or after the date of IE2 or IE3 will be assumed to have returned to baseline. For each imputed dataset, missing change from baseline data on or after IE2 or IE3 will be replaced by a value randomly drawn from a normal distribution $N(0, V_c)$, where V_c is the variance of change from baseline estimated from all other observed values without IE2 or IE3 at the corresponding visit, regardless of treatment groups, excluding those on or after the date of IE2 or IE3. A total of 30 datasets will be imputed.
 - Step 3: For each imputed dataset, the MMRM or ANCOVA model described below will be applied to each completed set and the inference will be drawn using Rubin's combination rules (SAS proc MIANALYZE).
 - MMRM: The mixed model includes the categorical fixed effects of treatment, visit and treatment-by-visit interaction, stratification factors (Advanced Therapies-IR status (yes vs no), baseline steroid use (yes vs no), and baseline Adapted Mayo score (≤ 7 vs > 7)), and the continuous fixed covariates of Baseline measurements. An unstructured variance covariance matrix (UN) will be used. If the model cannot converge, an autoregressive (1) covariance structure matrix will be used. The parameter estimations are based on the method of restrictive maximum likelihood (REML). The fixed effects will be used to report model-based means at corresponding visits.

- ANCOVA: For continuous efficacy variables that are collected at only one post-baseline visit, ANCOVA will be used. The model includes the categorical fixed effects of treatment, stratification factors, and the continuous fixed covariates of baseline and measurement.

9.3 Primary Efficacy Endpoint and Analyses

9.3.1 Primary Efficacy Endpoint

The primary efficacy endpoint is the achievement of clinical remission per Adapted Mayo score at Week 12.

9.3.2 Main Analysis of Primary Efficacy Endpoint(s)

The attributes of the estimand corresponding to the primary efficacy endpoint are summarized in [Table 1](#).

Table 1.**Summary of the Estimand Attributes of the Primary Efficacy Endpoint(s)**

Estimand Label	Treatment	Endpoint	Population	Attributes of the Estimand		Statistical Summary
					Handling of Intercurrent Events	
Primary	Risankizumab 1200 mg IV vs. placebo	Achievement of clinical remission per Adapted Mayo score at Week 12	ITT2	IE1: premature discontinuation of study drug. IE2: initiation or dose escalation of UC-related corticosteroids. IE3: occurrence of the UC-related surgery (ileostomy, colectomy, or proctocolectomy) All data after IE1 will be used. All subjects will be considered as non-responder on or after the date of IE2 or IE3.	IE1: premature discontinuation of study drug. IE2: initiation or dose escalation of UC-related corticosteroids. IE3: occurrence of the UC-related surgery (ileostomy, colectomy, or proctocolectomy) All data after IE1 will be used. All subjects will be considered as non-responder on or after the date of IE2 or IE3.	Proportion of subjects achieving clinical remission per Adapted Mayo score

The primary analysis of the primary endpoint will be conducted on ITT2 population based on randomized treatment groups (risankizumab 1200 mg IV vs placebo) using NRI-MI for missing data handling. Point estimate and 95% CI using normal approximation will be provided for the response rate for each randomized treatment group. The difference between the treatment groups (risankizumab 1200 mg IV vs placebo) in the primary efficacy endpoint will be assessed using the CMH test and will be stratified by Advanced Therapies-IR status (yes vs no), baseline steroid use (yes vs no), and baseline Adapted Mayo score (≤ 7 vs > 7). Point estimate, 95% CI and nominal p-value for the treatment comparison will be presented.

The following rules are used to calculate the stool frequency subscore (SFS) and rectal bleeding subscore (RBS) (ePRO specification document, [Appendix F](#)) in the primary analysis:

- Daily RBS is captured directly in the eDiary 'STOOL1-How often saw Blood in Stool'.
- Daily SFS is calculated by subtracting subject's normal number of bowel movements from the absolute daily stool frequency and assigning the following scores:
 - 0 = Equal to or less than Normal
 - 1 = 1-2/day more than normal
 - 2 = 3-4/day more than normal
 - 3 = >4 stools/day more than normal
- Note: The stool frequency subscore during days which the subject received anti-diarrheal medication will be scored as a 3.
- Define a 10-day period during which daily subscores are collected before the partial adapted Mayo score at each visit.
- Subscores will be calculated by averaging the 3 most recent valid Daily SFS & RBS within the 10-day period, excluding the day before endoscopy (due to bowel preparation), day of endoscopy and 2 days following the endoscopy (for visits that include an endoscopy). The calculated scores following these above rules will be recorded to an eCRF page by study sites that will be used in the primary analysis.

9.3.3 Sensitivity and Supplementary Analyses of the Primary Efficacy Endpoint

Tipping point analyses will be conducted as sensitivity analyses for the primary endpoint.

The above described CMH analysis will be repeated with the ITT2 population using AO data as a supplementary analysis.

In addition, the following sensitivity analysis will be conducted for the primary endpoint:

- The conflict in Ukraine may impact the treatment or follow-up of subjects in Ukraine and the surrounding region. Moreover, the conflict may also impact the quality of the data or the ability to verify the data. The above described

CMH analysis based on NRI-MI will be conducted with a subgroup of ITT2; ITT2 population excluding subjects who were impacted by the geo-political conflict in Ukraine or surrounding area.

- The above described CMH analysis based on NRI-MI will be conducted with the ITT2 population applying the following rules to calculate the stool frequency subscore and rectal bleeding subscore for the primary endpoint:
 - Define a 7-day period during which daily subscores are collected before the partial adapted Mayo score at each visit.
Note: The stool frequency subscore during days which the subject received anti-diarrheal medication will be scored as a 3.
 - The subscores should be calculated by averaging the daily subscores from within this 7-day period, excluding the before endoscopy (due to bowel preparation) and day of endoscopy (for visits that include an endoscopy).
 - A minimum of 3 consecutive days of completed diary entries or 4 nonconsecutive days are necessary (otherwise the score should be considered missing).

9.4 Secondary Efficacy Endpoints and Analyses

9.4.1 Secondary Efficacy Endpoints

The secondary efficacy endpoints are defined in Section [3.2](#).

9.4.2 Main Analyses of Secondary Efficacy Endpoints

The attributes of the estimands corresponding to the secondary efficacy endpoints are summarized in [Table 2](#).

Table 2. Summary of the Estimand Attributes of the Secondary Efficacy Endpoints

Attributes of the Estimand					
Estimand Label	Treatment	Endpoint	Population	Handling of Intercurrent Events	Statistical Summary
Categorical Secondary	Risankizumab 1200 mg IV vs. placebo	
Achievement of:
 
 • clinical response per Adapted Mayo score at Week 12 • endoscopic improvement at Week 12 • histologic endoscopic mucosal improvement at Week 12 • endoscopic remission at Week 12 • clinical response per Partial Adapted Mayo score at Week 4 • no bowel urgency at Week 12 • no abdominal pain at Week 12 • histologic endoscopic mucosal remission at Week 12 • no nocturnal bowel movements at Week 12 • no tenesmus at Week 12 	ITT2	
IE1: premature discontinuation of study drug.
 
IE2: initiation or dose escalation of UC-related corticosteroids.
 
IE3: occurrence of the UC-related surgery (ileostomy, colectomy, or proctocolectomy)
 
All data after IE1 will be used.
 
All subjects will be considered as non-responder on or after the date of IE2 and IE3.
	Proportion of subjects achieving each categorical secondary endpoint

Attributes of the Estimand					
Estimand Label	Treatment	Endpoint	Population	Handling of Intercurrent Events	Statistical Summary
Continuous Secondary	Risankizumab 1200 mg IV vs. placebo	Change from Baseline to Week 12 in Functional Assessment of Chronic Illness Therapy-Fatigue (FACIT-Fatigue)/in Inflammatory Bowel Disease Questionnaire (IBDQ) total score/ in number of fecal incontinence episodes per week/in number of days per week with sleep interrupted due to UC symptoms	ITT2	IE1: premature discontinuation of study drug. IE2: initiation or dose escalation of UC-related corticosteroids. IE3: occurrence of the UC-related surgery (ileostomy, colectomy, or proctocolectomy) All data after IE1 will be used. All data on or after the date of IE2 and IE3 will not be used for continuous endpoints.	Mean change from Baseline in each continuous endpoint
UC-related hospitalizations through Week 12	Risankizumab 1200 mg IV vs. placebo	Occurrence of UC-related hospitalization through Week 12	ITT2	IE1: premature discontinuation of study drug IE2: initiation or dose escalation of UC-related corticosteroids IE3: occurrence of the UC-related surgery (ileostomy, colectomy, or proctocolectomy) All data after IE1 will be used. All data after IE2 or IE3 will be used.	Proportion of subjects having at least one UC-related hospitalization through Week 12

The binary secondary endpoints will be analyzed based on ITT2 using the same approach as that for primary endpoint as specified in Section 9.3.2. Specifically, CMH adjusting for stratification factors will be used to construct the treatment difference, the associated

95% CI and p-value between risankizumab 1200 mg IV group and placebo group. The NRI-MI will be the primary approach for missing data handling in the analyses of binary secondary efficacy endpoints except for Occurrence of UC-related hospitalization, of which AO data will be used.

For UC-related hospitalizations through Week 12, to consider Missing-Not-At-Random (MNAR) assumption due to different dropout rates between treatment groups, a supplementary analysis will be performed based on exposure adjusted occurrence of UC-related hospitalizations through Week 12. Exposure adjusted occurrence of UC-related hospitalization will be analyzed based on incidence rates. Incidence rates for hospitalization will be calculated as the number of patients with the respective event divided by the time at risk. For patients with an event during the study period, time at risk is the patient-years (PYs) from the first dose date to the first event before Week 12. For patients without an event during Period 1, time at risk is PYs from first dose date to the end of study follow-up period, where the follow-up period starts from the first dose date to the last dose date in Period 1+ 140 days if prematurely discontinues the study drug without entering Period 2 or M16-066, or the first dose date of Period 2 or M16-066 if enters Period 2 or M16-066, whichever occurs earlier. The event date is defined as the date of admission to the hospital for hospitalizations. The incidence rate difference, 95% CI and p-value are calculated to evaluate the statistical significance of the difference between risankizumab 1200 mg IV group and placebo group using normal approximation to Poisson distribution. The analysis will be based on the AO data.

The continuous secondary endpoints will be analyzed based on ITT2 by RTB-MI with MMRM (for endpoints with more than one post-baseline visits) or with ANCOVA (for endpoints with one post-baseline visit) and the corresponding analyses are specified in Section 9.2.2. The least square (LS) mean and 95% CI for each randomized treatment group and the LS mean treatment difference, the associated 95% CI and the p-value between risankizumab 1200 mg IV group and the placebo group will be provided. Considering unequal variances due to the unequal sample size in the two treatment groups (2:1 randomization), a sensitivity analysis will be performed for continuous secondary

endpoints with only a single post-baseline measure using an ANCOVA model that estimates variance by treatment group.

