 - The tipping point analyses are two-dimensional, i.e., assumptions about the missing outcomes on each of the risankizumab group and the placebo group can vary independently. The response rate among those subjects with missing response is assumed to be p_0 for placebo group and p_1 for risankizumab group, and the response rate p_0 and p_1 systematically vary from 0% to 100% by every 10% respectively. Given a set of (p_0, p_1) , the subjects with missing response will be randomly assigned as responders or non-responders using binomial distribution to generate 30 imputed datasets, and the same CMH method used for the primary analysis will be performed on each of the imputed datasets to obtain the results for each comparison between the risankizumab group versus the placebo group. SAS PROC MIANALYZE will be used to generate the final inferences of the risk difference between risankizumab group and placebo group, using Rubin's rule.⁴
 - If one pair of (p_0, p_1) is found to reverse the study result interpretation in terms of p-value larger than 0.05, then the (p_0, p_1) is identified as the tipping point. The results for a grid of (p_0, p_1) combinations are provided in tabular format. Note that missing data on or after the date of the UC-related corticosteroids intercurrent event or on or after or the date of the UC-related surgery will be considered as non-responders and will not be imputed in the tipping point analysis.

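### The supplementary hospitalization rate is labelled an MNAR analysis but rests on non-informative censoring, and no other planned analysis varies the unobserved admission risk of subjects lost before Week 12

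*SAP*

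**What the plan says.** Sub-Study 2 SAP 9.4.2 adds a supplementary analysis of UC-related hospitalization, giving its purpose as "to consider Missing-Not-At-Random (MNAR) assumption due to different dropout rates between treatment groups, a supplementary analysis will be performed based on exposure adjusted occurrence". Its components are:

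- Estimator: "Incidence rates for hospitalization will be calculated as the number of patients with the respective event divided by the time at risk".
- Time at risk for patients with an event: "time at risk is the patient-years (PYs) from the first dose date to the first event before Week 12".
- Time at risk for event-free patients: from first dose to the start of Period 2 or M16-066 for those who continue, or to "the last dose date in Period 1+ 140 days if prematurely discontinues the study drug without entering Period 2 or M16-066".
- Inference: rate difference, confidence interval and p-value "using normal approximation to Poisson distribution".
- Data: "The analysis will be based on the AO data". SAP 9.2.1 defines as-observed analysis as leaving missing evaluations unimputed.

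The SAP does have a method that can depart from MAR. In 9.2.1, "The tipping point analyses are two-dimensional": the response probability among subjects with missing data is varied separately in each arm. Section 9.3.3 assigns it to one endpoint: "Tipping point analyses will be conducted as sensitivity analyses for the primary endpoint".

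**The concern.** Person-time adjustment is valid only if subjects who leave would have gone on at the event rate of those still observed in their arm. That is non-informative censoring. MNAR means that missingness still depends on the unobserved outcome after allowing for observed data. The SAP draws this line itself in 9.2.1, where MAR is defined by dependence on observed rather than unobserved values. Unequal dropout rates can arise under MCAR, MAR or MNAR, so they do not identify MNAR.

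Hospitalization is secondary endpoint 11, in the Holm-tested group of the type I error family (SAP 13.0). It is exempt from NRI-MI, so its main analysis carries no conservative imputation, and this rate is the only missing-data check named for it. Subjects lost with worsening colitis could plausibly have a raised admission risk. The study report could then present an endpoint in the confirmatory family as checked against MNAR when that check was not made.

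**Working it through.** **No figure to reproduce.** The documents state no hospitalization rate, dropout rate or power for this endpoint. The inputs below are assumptions, except the 84-day window (Week 12) and the 140-day rule.

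**Inputs.** 12-week risk p = 1% (risankizumab) and 5% (placebo); constant hazard on study; a fraction d of each arm leaves on Day 42 after a last dose on Day 28; hazard multiplied by k afterwards, with k = 1, 3, 5, 10. Dropout is 4%/12% or 4%/25% (risankizumab/placebo).

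**Formulas.**
- Hazard: h = -ln(1 - p)/84. Rate per 100 patient-years = h × 36525, giving 4.37 (p = 1%) and 22.30 (p = 5%), a difference of -17.93.
- True 12-week risk: (1 - d)p + d[1 - exp(-42h - 42kh)]. For placebo with d = 12% and k = 10: 0.88 × 0.05 + 0.12 × (1 - exp(-0.0513 × 5.5)) = 0.0735.
- Event-free discontinuers under 9.4.2: 28 + 140 = 168 days credited, against an 84-day event window.

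**Three cases.** A: ordinary censoring on the exit date. B: the 9.4.2 time-at-risk rule, with admissions after exit unobserved. C: the same rule, with admissions after exit captured up to Week 12.

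In case B, for placebo at 12% dropout, events per subject are 0.88 × 0.05 + 0.12 × 0.0253 = 0.0470. Mean credited time is 91.8 days. The rate is 0.0470/91.8 × 36525 = 18.7, against 22.30 with time censored at exit.

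Rate difference per 100 patient-years, beside the true risk difference in percentage points:

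| Dropout | k | True difference | A | B | C |
|---|---|---|---|---|---|
| 4%/12% | 1 | -4.00 | -17.93 | -14.60 | -15.77 |
| 4%/12% | 3 | -4.53 | -17.93 | -14.60 | -18.02 |
| 4%/12% | 5 | -5.03 | -17.93 | -14.60 | -20.19 |
| 4%/12% | 10 | -6.17 | -17.93 | -14.60 | -25.22 |
| 4%/25% | 1 | -4.00 | -17.93 | -11.50 | -13.73 |
| 4%/25% | 10 | -8.72 | -17.93 | -11.50 | -32.45 |

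**Reading the table.**
1. Where later admissions are unobserved (A and B), the estimate is the same for every k, because k appears in neither numerator nor denominator. This does not depend on the assumed figures.
2. Case B changes with the dropout rate, from -17.93 with no dropout to -14.60 and -11.50, even at k = 1, where exit is non-informative. The cause is the denominator: events stop counting at Week 12 while event-free discontinuers accrue time to 140 days after the last dose. Ending their time at last contact turns B into A and restores -17.93.
3. Case C moves with k because those admissions are data.

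**Direction.** In the table the true difference at k > 1 is larger than -4.0, so ignoring post-exit risk understates the benefit. It can go the other way. With risks of 3% and 5% and 12% dropout on risankizumab only, the true difference shrinks from -2.0 (k = 1) to -0.5 points (k = 10: 0.88 × 0.03 + 0.12 × 0.154 = 4.5%, against 5.0%). The rate estimate in A or B is again unchanged.

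**The case against.** The strongest reply is that stopping drug does not mean losing the hospitalization record. The protocol collects adverse events until 140 days after the last dose (6.1.4), a hospital admission is a serious adverse event (6.1.1.2), and subjects who leave early have a 140-day follow-up call (5.1). SAP Table 2 uses data after all three intercurrent events for this endpoint. Even a subject dosed only on Day 0 has planned collection to Day 140, past Day 84. This stands: the gap concerns only subjects lost to follow-up or withdrawing consent, and case C shows the estimate responding when admissions are captured.

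The aim named in 9.4.2 is also unequal dropout, and a person-time rate can correct for unequal follow-up. That stands under non-informative exit with a sound denominator (case A).

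A reader might therefore go too far and infer that the analysis gives the same answer however dropout differs, or that it checks nothing. The documents do not support that. Under the 9.4.2 rule the estimate shifts with dropout rates and with observed admissions; only the unobserved risk after loss of contact leaves it unmoved. Nor do they support inferring that the confirmatory hospitalization result is compromised: that test is the CMH analysis of as-observed data, and the rate is supplementary.

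Finally, the 9.2.1 tipping-point method cannot be copied unchanged. Its 10% steps are coarse for a rare event: at 12% placebo dropout, about 38 of 322 subjects are event-free at exit, so one step adds about 4 events, or 1.2 points. Its non-responder rule after corticosteroid or surgery events also conflicts with this endpoint's estimand. Both objections stand and shape the fix.

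**Conclusion.** The concern holds as a mislabelled analysis plus a missing one. The rate in 9.4.2 is an exposure adjustment under non-informative censoring. It cannot vary the unobserved admission risk of subjects lost before Week 12, and nothing else planned for this endpoint does. A related defect in the same paragraph is that event-free time at risk runs past the Week 12 event window, which dilutes the rate in whichever arm has more discontinuation.

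The invariance to unobserved risk is general. The magnitudes are illustrative: they rest on the assumed risks, dropout fractions, exit day and constant on-study hazard, and case B takes every dropout's later admissions as unobserved, an upper bound given the planned follow-up. The direction of error cannot be stated in advance, since it depends on which arm loses more subjects and on their risk. This is a minor, inexpensive correction.

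**What to change.** Three changes to Sub-Study 2 SAP 9.4.2:

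1. Delete the MNAR label and describe the rate as an exposure adjustment that assumes non-informative censoring.
2. End event-free time at risk at the earliest of Week 12, last contact, or first dose of Period 2 or M16-066. This aligns the denominator with the event window, settles the ambiguous earliest-date wording, and covers subjects who complete dosing without rolling over, for whom no explicit rule is given.
3. Add a two-dimensional tipping-point analysis for subjects lost before Week 12 with no recorded event, varying the probability of a later admission (p0, p1) independently by arm and using the same CMH method. Use a finer grid at low probabilities, for example 1-2% steps (at 12% placebo dropout, a 2% step adds about 0.75 events, or 0.2 points). Keep observed data after corticosteroid or surgery events, as Table 2 requires.

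The cost is one extra supplementary table and minor reprogramming of the tipping-point code planned for the primary endpoint. The confirmatory test and the alpha allocation do not change.
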